#### 4.2 Drug/Device Handling:

Psilocybin is a tryptamine derivative presenting as a white crystalline solid with a melting point of 220-228°C. It is stable over extended periods in dark storage at controlled room temperature. Psilocybin is soluble in 20 parts boiling water or 120 parts boiling methanol. For use in clinical studies, psilocybin is provided as 25 mg capsules (white opaque, Capsugel Vcaps Plus HPMC size 2). Psilocybin will be obtained from Usona Institute in Madison, WI and stored in the Investigational Drug Service (IDS) Pharmacy at UMN. UMN IDS will handle all psilocybin allocation and storage, and will provide the compound as needed for each testing session. We will create a system which will allow the IDS staff to enter variables necessary for our minimization randomization procedure as described which will allow the IDS staff to determine the participant's group to ensure the double blind. All participants, family members, and the entire research team will be blinded to testing group and order.

The active placebo niacin, also known as vitamin B3, is provided as 100 mg capsules (white opaque, Capsugel Vcaps Plus HPMC size 2). Niacin is United States Pharmacopeia (USP)-grade and also provided by Usona in the same capsules to maintain the blind.

Within the week of the dosing/testing session at the CRU, one of the MD psychiatrists will formally request the study drug using the IDS calendar system. One person from the study team that will be running the testing session, plus one member of the CRU clinical staff, will

## MEDICAL PROTOCOL (HRP-590)

PROTOCOL TITLE: VISUAL SURROUND SUPPRESSION UNDER PSILOCYBIN

VERSION DATE: May 18, 2023

walk over to IDS together to receive the study drug and bring it to the participant. Any unused product will be immediately returned to IDS.

4.3 Biosafety: N/A

4.4 Stem Cells: N/A

4.5 Fetal Tissue: N/A

## 5.0 Procedures Involved

### 5.1 Study Design:

The study involves a randomized, double blind, placebo controlled, crossover design with two different groups pairing the psychoactive drug psilocybin, or the active placebo Niacin, with a combination of perceptual tasks.

Randomization and Double-Blind: Participants who meet criteria for entry into the study (based on the telephone screen and the clinical interview) and consent to participate will be randomized to *psilocybin first (group A) or niacin first (group B)*, using an adaptive minimization randomization method. The purpose of the procedure is to ensure that the 2 groups are similar with respect to *age and gender*. Specifically, the minimization procedure will balance age groups (45 years or below/above 45 years) and gender. Following the evaluation, the study coordinator will share numerical values for these variables along with the subject ID number through a secure system (Box Secure Storage) with the study statistician who will use participant information to assign a blinded randomization group (A or B) using the minimization procedure.

The study statistician will then pass the blinded group assignment to IDS. Before the first participant is randomized, IDS will randomly assign “psilocybin first” “niacin first” to the letters A, and B; this assignment (of group to treatment letter) will not be communicated to anyone outside of IDS until the study is complete and the study team is ready to break the blind. Randomization will occur after Visit 1 (Day 0), when it is confirmed all eligibility criteria are met and before Visit 2, with a maximum 30-day window between them.

Participants will have one training/baseline session, followed by 2 experimental sessions in randomized order for each of the drug conditions (psilocybin or niacin placebo). We will test subjects under the influence of 25mg of psilocybin (**condition 1**) or 100mg of active placebo control (niacin or, **condition 2**).

We will test two groups for each of these conditions. Group A will be given psilocybin first, and active placebo Niacin second (N=20) and tested on surround suppression and EEG recording starting at 2 hours after ingestion of the experimental compound. Group B will be given niacin on their first dosing day and psilocybin on their second dosing day (N=20) and tested on surround suppression and EEG recording starting at 2 hours after ingestion of the experimental compound.

## MEDICAL PROTOCOL (HRP-590)

### PROTOCOL TITLE: VISUAL SURROUND SUPPRESSION UNDER PSILOCYBIN

VERSION DATE: May 18, 2023

Furthermore, this study will be conducted in two phases. A pilot phase ( $n=6$ ) will be completed before full study. For this phase, we will enroll an initial 6 subjects to work through the feasibility of implementing the study design, and to determine if any modifications need to be made for the full study design. We will start off slow and only enroll a single participant for the first 1-2 participants to test out the full protocol and closely monitor any potential problems that may arise that would need to be modified or removed from the design. See section 5.3 for more information on this pilot phase. Once this phase is complete, we will commence with the full study. See Figure 1.

[figure not shown]

Figure 1. Timeline of study design for the A) pilot phase to test the feasibility of the protocol prior to initiating the B) full study design in our cohort.

### 5.2 Study Procedures:

**Additional Procedures for COVID Screening.** Participants and study personnel (e.g. staff, students, volunteers, or anyone with direct participant contact) will adhere to institutional guidelines around COVID-19 risk and safety and adjust our precautions accordingly as they evolve. These guidelines will be communicated to the participants at the time they are in effect, and implemented accordingly.

**Initial Survey and Phone Screening.** Interested candidates will be contacted through a survey in REDCap to gather preliminary eligibility criteria and contact information (see Appendix A), and

## MEDICAL PROTOCOL (HRP-590)

### PROTOCOL TITLE: VISUAL SURROUND SUPPRESSION UNDER PSILOCYBIN

VERSION DATE: May 18, 2023

interested participants that meet our basic inclusion criteria will be contacted via phone or Zoom to determine if they meet additional criteria for scheduling an in-person interview to determine final eligibility and enrollment. Phone screens will be conducted by the study coordinator and will adhere to an approved phone script (see Appendix B). All study visits and assessments performed remotely over the phone or Zoom will have both audio and video recordings (when applicable) of each visit.

#### **VISIT 1:**

**In-person consent/interview screening.** Participants that pass the survey and telephone screens will be invited to the ARC to be consented and interviewed by the research coordinator, to be consented and tested. Participants will be screened on the assessments outlined below to determine final eligibility for enrollment into the study. Participants will receive a physical exam to assess overall health, urine for pregnancy testing, as well as blood draws to screen for blood-based biomarkers of major health problems and for baseline cytokine levels, a diagnostic interview with the MINI-7 to assess presence or history of mental illness and substance abuse, and a review of their personal and family medical history, and measure weight and vitals. Blood draws for health screening at baseline will be collected in green top tubes containing lithium heparin as an anticoagulant, and 2.5mL of blood will be collected and analyzed at the UMMC West Bank Children's Hospital lab. Blood draws for cytokine testing will be collected in red top serum separator tubes that contain a clot activator but no anticoagulants, preservatives, or separator material, and we'll collect 6mL of whole blood per participant. Participants will be screened for uncontrolled hypertension with two separate measurements of blood pressure using a blood pressure cuff during their visit. They will be brought in for a second visit (visit 1b) within 1 week of visit 1a to obtain two additional blood pressure measurements to assess whether they have uncontrolled hypertension, which will be determined if their average blood pressure across the 2 days and 4 measurements is greater than 140/90mmHg. We will also collect ECG data to test whether they have a QTc greater than 450 msec, based on the [FDA Guidance of Clinical Evaluation of QT/QTc Interval Prolongation and Proarrhythmic Potential for Non-Antiarrhythmic Drugs](#). Those that do have a QTc greater than 450 msec will be excluded from the study.

Candidates who do not meet all of the inclusion and/or one or more of the exclusion criteria will not be enrolled into the study.

**Clinical Assessment.** Assessment interviews will be conducted by trained research team members, directly after the consent process.

*Assessment of General Psychopathology and Demographic Information (Zoom option).* To describe our sample and to determine criteria for ineligibility, we will screen for the presence of Diagnostic and Statistical Manual of Mental Disorders-5th edition (DSM-5) (American Psychiatric Association, 2013a) psychiatric diagnoses (American Psychiatric Association, 2013b) using the MINI-7 (Sheehan et al., 1998). We will also administer the Adverse Childhood

## MEDICAL PROTOCOL (HRP-590)

### PROTOCOL TITLE: VISUAL SURROUND SUPPRESSION UNDER PSILOCYBIN

VERSION DATE: May 18, 2023

Experience (ACE) questionnaire, which is a 10-item assessment of childhood abuse that predicts health concerns in adults (Feliti et al., 1998). Clinicians formulate the diagnosis combining all clinical information. Following the clinical evaluation, the study team will review all clinical information and determine final eligibility to decide whether the participant will move forward to randomization.

#### Neurocognitive assessments.

- The Wechsler Abbreviated Scale for Intelligence-II will be used to estimate intellectual functioning (*in person*). An add-on will be used during the Matrix Reasoning subtest to test for divergent thinking, a form of creative thinking and cognitive flexibility used in other psychedelic research studies (Kiraga et al., 2021). In addition to the standard response about which answer is correct, participants will be asked to provide alternative answers they think also might be correct.
- The 5D-ASC (*Zoom option*) is a 94-item questionnaire that measures altered states of consciousness, and consists of 5 dimensions/subscales (Dittrich, 1998), including “Oceanic Boundlessness” (27 items), “Anxious Ego Dissolution” (21 items), “Visionary Restructuralization” (18 items) “Auditory Alterations” (15 items) and “Reduction of Vigilance” (12 items). This validated scale has been used in multiple research studies aiming to understand the subject experience of psychedelic drugs (Carhart-Harris et al., 2016; Hasler et al., 2004; Hysek and Liechti, 2012; Liechti et al., 2017; Schmid et al., 2014; Vollenweider et al., 2007; Vollenweider and Kometer, 2010).
- The RMEQ-30 (*Zoom option*) is a 30-item measure that consists of 4 orthogonal dimensions that represent different aspects of a mystical experience, including mystical experiences, positive mood, transcendence of space and time, and ineffability (Barrett et al., 2015; Maclean et al., 2012). Previous work has linked certain domains of the mystical experience with positive outcomes (Garcia-Romeu et al., 2014; Griffiths et al., 2018; MacLean et al., 2011).
- The PANAS (*Zoom option*) is a self-report of positive and negative affect and has been used in both clinical and nonclinical populations to measure mood affect (Crawford and Henry, 2004; Watson et al., 1988).
- The 5-factor personality inventory (NEO-FFI) (Costa and McCrae, 2008) (*Zoom option*) will be administered at baseline testing, as well as at the final follow up session. Previous research with psilocybin in healthy volunteers has shown that mystical experiences occasioned by psilocybin in the appropriate set and setting leads to increases in the openness domain of the NEO-FFI (MacLean et al., 2011), and that those who score higher on the neuroticism domain may be more prone to difficult experiences on psilocybin (Barrett et al., 2017) and may require more attention during parts of the dosing session.
- We will also administer the Ego-Dissolution Inventory (EDI) to participants (*Zoom option*), which is a validated assessment of both ego dissolution (ED) and ego-inflation (EI) applied in previous psilocybin research (Nour et al., 2016). Ego dissolution has been

MEDICAL PROTOCOL (HRP-590)

PROTOCOL TITLE: VISUAL SURROUND SUPPRESSION UNDER PSILOCYBIN

VERSION DATE: May 18, 2023

correlated to improved mental health outcomes associated with psilocybin-occasioned experiences.

- BVMT-R™, which has been used to measure changes in cognitive function linked to neuroplasticity in schizophrenia patients undergoing targeted cognitive training (Fisher et al., 2009; <https://www.parinc.com/Products/Pkey/30>). BVMT-R measures visuospatial memory where participants are shown a stimulus page and asked to draw as many of the figures as possible in their correct location on their own page, and then retested 25 minutes later for memory recall, followed by a recognition trial where they are asked which of the figures were included in the original stimulus.
- HVLT-R™ has also been used to measure changes in cognitive function linked to neuroplasticity in schizophrenia patients undergoing targeted cognitive training (Fisher et al., 2009; <https://www.parinc.com/Products/Pkey/130>). HVLT-R is a word-list learning and memory test.
- EBI has been developed and used in psilocybin clinical trials to measure emotional breakthrough, which has been linked to longer term changes in psychology function (Roseman et al., 2019).

**Neuroimaging Procedures.** All brain imaging will be completed at the CMRR on a 3T whole body Siemens MAGNETOM scanner (Siemens Medical Solutions, Erlangen, Germany) using a standard Nova coil. We will take a series of scans during a single session to collect structural and functional fMRI data. Data will be collected from participants during baseline assessment and within 24 hours following each dosing day, and again at 3-4 days and 7 days after each dosing session for a total of 7 scans per participant. After an initial structural scan, we will collect resting state fMRI to test changes in BOLD signal in brain networks known to be impacted by psilocybin and other 5HT2A receptor mediated psychedelics, including the default mode network (Carhart-Harris et al., 2014). Heart rate and respiratory rate data will also be collected during the scan to account for artifacts that may confound results during resting state scan. We will then perform a series of task-based scans using the same visual tasks tested during the EEG dosing session (*SEE Psychophysics section under Visits 2 and 4*). We will then perform a diffusion-weighted MRI (dMRI) scan to look for changes in structural connections in white matter, which has been shown previously in animal models with serotonergic psychedelics (Ly et al., 2018). Data will be processed using standard software packages (e.g., the FMRIB Software Library (FSL - FslWiki)), which is an open-source software library that contains tools for statistical analysis and image processing for MRI brain imaging data).

The same study procedures, except consent, demographics and medical history will be performed at Visits 3, 5, 6 and 7. Pregnancy test will be collected on Visit 1, 2, 3, 4, and 5. EEG and psychophysics will be collected on visits 2, 4, and 6, and fMRI will be collected on Visits 1, 3, and 5. Regarding blood draws, two separate tubes of blood will be collected at Visits 1, 3, and 5 for serum chemistry and cytokine assays.

## VISITS 2 and 4

MEDICAL PROTOCOL (HRP-590)

PROTOCOL TITLE: VISUAL SURROUND SUPPRESSION UNDER PSILOCYBIN

VERSION DATE: May 18, 2023

**Dosing Session.** Dosing sessions will involve 8 hours of preparatory visits (2a-d) before the day of the first dosing session, and one hour before the second dosing session (4a), which will occur either in person in the dosing room in CRU or over Zoom if preferred, and will be recorded for both audio and video. During these 4 preparatory visits, which will last approximately 2 hours each prior to the first dosing session, and 1 hour prior to the second dosing, for a total of 9 hours, participants will meet with at least one of their dosing session monitors that will be sitting with them, and discuss what to expect during the dosing session, and what food preferences they have for two meals they will be offered during their time in the CRU. This visit also serves to help build rapport and common understanding between the two monitors and the participants prior to the dosing session, to review the participants personal history and anything that might come up during the dosing sessions (see visual aid that will be used for this in Appendix H), as well as an opportunity to educate the participants more on the procedures that will occur during the day, and the purpose of the study and the characteristics of the study drug. Participants will be asked to get at least 6-8 hours of sleep, and get dropped off in the morning by a trusted familiar individual. Once checked and settled into the room, participants will be allowed the option to remove their mask during the day, if that feels more comfortable for them. Prior to the administration of psilocybin or placebo, the participants will be given a brief physical exam, including a pregnancy test, breathalyzer for alcohol content, and measuring weight and vital signs. Participants will then be asked to answer a few questions on a checklist about their substance use since being enrolled in the study to assess whether they have engaged in activities that would make them ineligible and withdrawn from the study (see Appendix C). If they pass, we will proceed to the dosing session after a team member from the CRU and one of the study team members will walk over to IDS to receive the study compound, and escort it back to the testing room. The dosing sessions will be recorded using video equipment in the room for the duration of the visit.

Participants will undergo baseline testing for outcome measures and preparatory interviews with the co-facilitators of the dosing sessions. On each of the testing day sessions (approximately 8 hours each), a hospital room in the CRU will be set up to create the optimal setting for a psychedelic experience, per the guidance and recommendations of other researchers performing work with these compounds in controlled clinical settings (Johnson et al., 2008). The room will not have windows, and will be equipped with a private bathroom in the room for when participants need to excrete urine, feces or vomit. The hospital bed will be set up with blankets and pillows to keep participants comfortable. We will place decorations around the room with neutral art/photographs of nature, and will have the participants bring some personal item with them that they find helpful for their own well-being (this may vary, but could include a stuffed animal, a sacred item or other totem that they use to help in their past experiences in altered states of consciousness).

Participants will receive a 25mg/70kg dose of psilocybin, or 100mg dose of the niacin placebo, in a private, quiet space and encouraged to focus their attention inward for the majority of the experience, using eye shades and headphones with instrumental music. Participants will be lying on a comfortable surface. At least two monitors will be present for the duration of the participants stay in the research unit to monitor them. One of those monitors

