### 1.1 Specific Aims:

**Aim 1a will test the acute impact of psilocybin on the strength of the psychophysical surround suppression effect.** Healthy volunteers will complete a visual task at baseline (pre-drug administration) and again after either an oral dose (25mg) of psilocybin or Niacin (100mg) placebo control (baseline, 2 hours post-drug administration, 2 week followup). The psychophysical measurements are made via forced-choice binary (yes/no) responses to questions about participants' perceptions of visual stimuli. The data collected from this Aim will provide a psychophysical characterization of the impact of psilocybin on visual surround suppression.

**Aim 1b will test the acute impact of psilocybin on the strength of known surround suppression-related vERPs measured with EEG.** Neural data will be collected as participants complete the visual tasks in Aim 1a (baseline, 2 hours post-drug administration, 2 week followup). The data collected will provide a neurophysiological characterization of the effect of psilocybin on the target vERPs commonly associated with visual surround suppression.

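### The protocol gives two psilocybin doses, a fixed 25 mg and a weight-scaled 25 mg per 70 kg, and describes only a 25 mg capsule, so the treatment under test is not uniquely defined

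*Combined protocol and SAP*

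**What the plan says.** Four places in the current protocol (version of May 18, 2023) bear on the dose.

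- **Section 1.1, Aim 1a:** the visual task is repeated "after either an oral dose (25mg) of psilocybin or Niacin (100mg) placebo control". There is no weight term.
- **Section 5.1, Study Design:** "We will test subjects under the influence of 25mg of psilocybin" (condition 1), against 100 mg of niacin (condition 2). There is no weight term.
- **Section 5.2, Visits 2 and 4, Dosing Session:** "Participants will receive a 25mg/70kg dose of psilocybin, or 100mg dose of the niacin placebo". Here the psilocybin dose carries a weight term and the niacin dose does not.
- **Section 4.2, Drug/Device Handling:** "For use in clinical studies, psilocybin is provided as 25 mg capsules". Niacin "is provided as 100 mg capsules (white opaque, Capsugel Vcaps Plus HPMC size 2"), the same capsule type as psilocybin, and this sameness is given as the means of keeping the blind.

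Section 5.2 also lists the checks made before dosing, "including a pregnancy test, breathalyzer for alcohol content, and measuring weight and vital signs", but does not link the weight to any dose calculation. The revision history records no change of dose.

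**The concern.** The amount of study drug each participant receives should have one answer in a protocol, and here it has two. Both are in operative text, so this is not a difference between an amendment log and the current wording.

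Three things depend on the answer:

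- **Exposure.** The protocol itself treats psilocybin's effects as dose-related: Section 2.2 says so for perceptual change, the domain of the primary endpoint, and Section 4.1 for headache. A result or safety profile cannot be tied to a dose that is not defined.
- **Consistency.** If one text were followed for some participants and the other for the rest, two regimens would be mixed in one trial. Among those given the scaled dose, milligrams would rise with body weight, so dose and weight could not be separated when participants are compared. The covariates named in Section 15.3 are treatment order, age and sex, plus other baseline predictors that differ between groups. Neither body weight nor milligrams given is named.
- **The blind.** A weight-scaled amount could call for a different number or strength of psilocybin capsules, set against a single fixed niacin capsule.

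**Working it through.** **Inputs**

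- Fixed rule: 25 mg (Sections 1.1 and 5.1).
- Scaled rule: 25 mg per 70 kg (Section 5.2), that is 25/70 = 0.357 mg/kg.
- Psilocybin capsule: 25 mg, the only strength described (Section 4.2).
- Body weight: not given. Sections 8.1 and 8.2 set no weight or BMI limit. A range of 50 to 120 kg is assumed for illustration.

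**Formulas**, with w the body weight in kg

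- Scaled dose = 25 × w/70 mg
- Difference from the fixed dose = w/70 − 1
- Capsules needed = scaled dose/25 = w/70
- Dose per kg under the fixed rule = 25/w mg/kg

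**Results**

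| Weight (kg) | Scaled dose (mg) | Difference from 25 mg | 25 mg capsules | Fixed 25 mg, as mg/kg |
|---|---|---|---|---|
| 50 | 17.9 | −28.6% | 0.71 | 0.500 |
| 60 | 21.4 | −14.3% | 0.86 | 0.417 |
| 70 | 25.0 | 0% | 1.00 | 0.357 |
| 80 | 28.6 | +14.3% | 1.14 | 0.312 |
| 90 | 32.1 | +28.6% | 1.29 | 0.278 |
| 100 | 35.7 | +42.9% | 1.43 | 0.250 |
| 120 | 42.9 | +71.4% | 1.71 | 0.208 |

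The two rules coincide only where w/70 = 1, at 70 kg.

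**Supply.** The scaled dose is a whole number of 25 mg capsules only when w is a multiple of 70. Within the assumed range that is 70 kg alone. Section 4.2 gives no rule for splitting, compounding, rounding or combining capsules, nor for matching the niacin capsule to a varying psilocybin amount.

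**Information flow.** Under Section 5.1 the statistician receives the values for age and gender with the subject ID, and passes the group letter to the pharmacy. No section describes a body weight reaching the pharmacy that supplies the capsules.

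The scaled rule therefore cannot be carried out from the supply and procedures as described. The contradiction does not enter the sample-size statement in Section 15.2.

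**The case against.** The best defence is that three of the four places (Sections 1.1, 4.2 and 5.1) are consistent with a fixed dose, so the weight term in Section 5.2 may be leftover wording. The documents do not say so. In addition, the weight term is attached to psilocybin only, and weight is measured before staff collect the compound from the pharmacy. Weight-scaling therefore cannot be ruled out from the text.

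Four narrower objections have some force.

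- **Mixed regimens are a risk, not a finding.** The pharmacy handles allocation and a psychiatrist requests the drug, so any ambiguity would act mainly at ordering and dispensing. Those instructions are not among the documents, and nothing shows that mixing has occurred.
- **Silence on preparation is not proof that it is impossible.** The supportable statement is that no method is described. The effect on the blind is likewise conditional on the scaled rule being followed.
- **The drug contrast is within person.** Each participant is scheduled to receive both compounds, and the mixed model has a random intercept by participant. Weight is nearly constant within a person, so it does not confound the psilocybin–niacin comparison. What suffers is the definition of the dose, the spread of exposure between participants, and interpretation.
- **The weights are assumed.** The −29% to +71% range follows from choosing 50 and 120 kg and is not an expected dosing error.

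None of these removes the contradiction between the dose statements.

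**Conclusion.** The concern holds, and the correction is mandatory. Two incompatible rules define the psilocybin exposure, no text reconciles them, and the only capsule strength described matches one body weight in the illustrated range under the scaled rule.

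At the assumed weights the rules differ by −29% (17.9 against 25 mg at 50 kg) to +71% (42.9 against 25 mg at 120 kg). The contradiction itself does not depend on those weights; only its illustrated size does. The within-person treatment comparison is not shown to be biased. What is undefined is the dose to which the efficacy and safety results refer, and whether it can be given under blind. This review does not say which rule is right.

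**What to change.** 1. Reconcile Sections 1.1, 4.2, 5.1 and 5.2 (Visits 2 and 4, Dosing Session) so that one dosing rule, chosen by the sponsor, appears everywhere.
2. Confirm in Section 4.2 that the supplied psilocybin and niacin capsules can deliver that rule under blind, and describe any preparation or matching it requires.
3. Confirm that the case report form records the milligrams actually given at each dosing session, and add the field if it does not.
4. If any participant was dosed under the other reading, record the amount and report it with the results.

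The cost is one protocol clarification or amendment and at most one case report form field. The sample size does not change.
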